**Figure 4. Study design**

\* PROMs (patient reported outcome measures): will also be applied in both groups at end RT and at end RT + 4 weeks

Consenting, eligible patients will be included when admitted to planning of RT. Baseline assessments will be performed by a project nurse/the PhD student at start of RT. As we believe that the intervention may have both a short- and long term impact on patients' QoL and functioning, the patients will be followed for 52 weeks with specific study assessments and for survival up to 5 years. The main outcomes assessments will take place at 8 and 16 weeks after the end of RT. A blinded assessor will be used to assess outcomes other than those that are patient reported (**PROMs**) at these time points.

## Patients

Patients will be consecutively recruited at the RTU, Gjøvik and St. Olavs hospital.

### The inclusion criteria are:

- ≥65 years of age
- confirmed cancer diagnosis (histology/cytology)
- living in one of the participating municipalities in the catchment area of SI or in the municipality of Trondheim
- referred for palliative or curative RT
- fluency in Norwegian, orally and in writing
- ability to fill in self-report questionnaires
- provide written informed consent

### The exclusion criteria are

- severely ill with a life expectancy < 3months
- referred to receive one fraction of RT only (one day treatment)

## Outcomes and assessments

*The effectiveness of the intervention* will be tested by the use of patient-reported measures and tests for physical performance/mobility. Additionally, the use of health care services will be

 A minor change of the inclusion criteria were made by February 2020 to include patients with a cancer diagnosis without cytological/histological confirmation, i.e. in cases where the referring oncologist affirmed the malignant diagnosis based on medical history, imaging and blood analyses, see attached amendment.

registered and evaluated. The pre-defined primary time point for outcome assessment is 8 weeks post-RT.

Physical function (PF) measured by the European Organisation for Research and Treatment of Cancer (EORTC) Quality of life Questionnaire-C30 (QLQ-C30)(30) is the defined primary outcome.

Secondary outcomes are:

- QoL assessed by the EORTC QLQ-C30 global QoL scale and EQ-5D-5L(31)
- Physical performance/mobility assessed by the following performance tests: Short Physical Performance Battery (SPPB)(32), Timed Up and Go test(33), Grip Strength (measured by a dynamometer)(34), and one legged balance test (35)
- Use of health care services (hospital in- and outpatient services and municipality services in terms of home care, nursing home care and use of other services such as physiotherapist, occupational therapists, and rehabilitation programs)

Other defined outcomes:

- Symptom occurrence assessed by the EORTC QLQ-C30, specifically fatigue, pain, dyspnea, and sleeping disturbances
- Emotional function assessed by the EORTC QLQ-C30
- Nutritional abnormalities assessed by BMI, weight loss and loss of appetite (subscale of the EORTC QLQ-C30).

Patient reported outcomes (EORTC QLQ-C30 and EQ-5D-5L) will be assessed at baseline, by the end of RT, and thereafter 4, 8, 16, 32 and 52 weeks after RT. Performance tests will be applied at baseline and 8 and 16 weeks after the end of RT. Data on primary care service utilization (home based and institutional care) and hospital services will be registered throughout the intervention period and during follow-up (one year, week 52).

*Feasibility* will be assessed by a process evaluation aiming to identify facilitators and barriers for a successful implementation, using mixed methodology. Measures recommended for each patient's intervention plan will be consecutively registered, as will patients' compliance and adherence through weekly contact with the coordinating nurse (log notes). Further data will include interviews with patients and provider. Questionnaires to involved primary health care nurses and other relevant professionals will also be applied.

*Economic evaluation* will be based on a comparison of costs and effects as measured by the main outcome measures, EQ-5D-5L particular. Costs include direct costs associated with GAM (intervention costs), as well as costs related to hospital admissions, home care and nursing home care. Data on service utilization will be obtained from hospital and municipal registers, respectively. Both intervention costs (GAM) and conventional care will be calculated in detail..

#### **Sample size**

Sample size estimations are based on a block-randomised cluster RCT. A total of 57 patients distributed in 16 clusters (proportionally to cluster size) in each group will enable the detection of a clinically significant difference (12 points)(36) on the physical functioning QLQ-C30 scale with a standard deviation (SD) of 22 at the significance level of 5% and a power of 80%, given an intracluster correlation (ICC) of 5%. The ICC is assumed to be small

---

 For detail see statistical analyses plan dated 12-3-19 and protocol amendment dated 9-3-20.

as the intervention primarily will be applied by municipal cancer nurses with similar training in collaboration with hospital specialists, similar to all intervention patients. According to a former study on older cancer patients by this study group, we expect an attrition of about 15-20% at 16 weeks of follow-up post-RT. Furthermore, it is paramount to ensure that all municipalities are represented by included patients. To take this and attrition into account, we aim at including 81 patients in each group, i.e. a total of 162 patients. See also statistical analyses plan dated 12-3-19 and attached protocol amendment dated 9-3-20.

## Statistics

---

All analyses will be pre-planned in collaboration with the study statistician before start of the study, and will follow the intention-to-treat principle. Descriptive statistics will be used to investigate quantitative data related to feasibility, compliance and adherence. Associations will be assessed by using suitable regression models. Interviews will be analysed by an interpretative approach, aiming at capturing interviewees' experiences with the intervention. To investigate the intervention effect, the trend in pre-defined outcomes will be compared between intervention and control groups by estimating linear mixed models accounting for intra-patient (due to repeated measurements per patient) and intra-municipality variations. The results will further be adjusted for relevant covariates.

Due to the potential heterogeneity of the study sample, the effect of the intervention will also be tested against a retrospectively matched control group, extracted from the observational study in the first part of the overarching project (see Fig 1). Patients in the foregoing observational study have given their consent to this comparison, and the observational study makes use of the same patient-related outcome measures, assessed on the same points of time as the current study.

For the economic evaluation, we measure outcome in terms of Quality Adjusted Life Years (QALY) by combining the preference based Health Related Quality of Life index from EQ-5D-5L and the corresponding time periods. We evaluate cost-effectiveness by estimating the incremental cost-per-QALY ratio defined as the mean cost per patient for the intervention group minus mean cost per patient for the control group, divided by mean QALY intervention group minus mean QALY control group. We apply non-parametric bootstrapping methods to assess uncertainty and use cost-effectiveness plane and cost-acceptability curves for presentation of results.

See also detailed statistical analyses plan dated 12-3-19.

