## **Setting**

---

The primary study center is the Radiotherapy Unit (RTU) at SI providing RT to the population in Oppland and Hedmark counties (380 000 inhabitants), and treating about 700 patients per year, 2/3 are  $\geq 65$  years. Palliative RT represents about 60 % of the patients, and is administered independent of diagnosis. Curative treatment is given to breast, prostate, lung and skin cancers only. Hedmark and Oppland comprise 48 municipalities, and 30 of these have consented to participate in the present study. The RTU, St Olavs hospital, Trondheim will be the second study center. This RTU provides all RT services to the inhabitants in the catchment area including Trondheim municipality (180 000 inhabitants). RT is administered to about 250 patients  $\geq 65$  years from Trondheim per year. The municipality of Trondheim is organized into 4 health care districts.

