## **Design**

---

[figure not shown]
The present study is a controlled cluster-randomized pilot study. Cluster-randomization is chosen to avoid contamination of the control group. It is paramount that control and intervention patients are not handled by the same primary health care professionals, and this can only be achieved by randomizing municipalities (or health care districts).

Before patient recruitment commences, a selection of 32 municipalities/city districts (= clusters) will be stratified into blocks in accordance with number of inhabitants. The selection will include city districts, large and smaller municipalities to ensure sample size and representativity. Clusters within each block will be randomly assigned to one of the groups by using a computer-generated code, 16 in each group.

Eligible patients from clusters assigned to intervention will enter the intervention group and enter the intervention program. Patients from control clusters will enter the control group.

These patients will receive treatment and care in accordance with usual routines and standards

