We will calculate the intervention cost based on a micro-costing approach. Cost-effectiveness of the intervention will be evaluated by calculating the incremental cost-effectiveness ratio (ICER) that is the difference in mean costs divided by the difference in mean Quality

Adjusted Life Years (QALYs). We calculate QALYs by an area under the curve approach under the assumption of piecewise linear change in EQ-5D-5L-index values over time. Missing data will be imputed by multiple imputation and the uncertainty of the ICER will be assessed by performing sensitivity analysis including application of bootstrapping techniques.

Feasibility

Feasibility will be assessed by a process evaluation aiming to identify facilitators and barriers for a successful implementation, using mixed methodology. Measures recommended for each patient's intervention plan will be consecutively registered, as will patient's compliance and adherence through weekly contact with the coordinating nurse (log notes). Further data will include interviews with patients and providers. Questionnaires to involved primary health care nurses and other relevant professionals will also be used.

Sample size

Sample size estimations are based on a block-randomized cluster RCT. A total of 53 patients distributed in 16 clusters (proportionally to cluster size) in each group will enable the detection of a clinically significant difference (12 points)⁸ in the physical functioning QLQ-C30 scale at week 8 with a standard deviation (SD) of 24 in each group at the significance level of 5% and a power of 80%, given an intra-cluster correlation (ICC) of 10%. The ICC is assumed to be small as the intervention primarily will be applied by municipal cancer nurses with similar training in collaboration with hospital specialists, similar to all intervention patients. Power calculation was performed for analysis of covariance, adjusting difference between groups for baseline values, and assuming the correlation between baseline and follow-up measurements to be 0.5. According to a former study on older cancer patients by this study group, we expect an attrition of about 15-20% at 16 weeks of follow-up post-RT. Furthermore, it is paramount to ensure that all municipalities are represented by included patients. To take this and attrition into account, we aim at increasing sample size by about 28% and including 81 patients in each group, i.e. a total of 162 patients.

References

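### The cost-effectiveness analysis states no baseline, stratum or cluster term and no bootstrap resampling unit, although clusters were randomised and EQ-5D-5L itself is modelled with baseline and cluster terms

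*Protocol*

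**What the plan says.** **Economic analysis.** The protocol (Statistics) takes the mean cost difference between groups, "divided by mean QALY intervention group minus mean QALY control group". On uncertainty it says "We apply non-parametric bootstrapping methods to assess uncertainty" and will "use cost-effectiveness plane and cost-acceptability curves for presentation of results". The SAP repeats the ratio of mean differences in its list of secondary outcomes and under Economic evaluation. It adds "We calculate QALYs by an area under the curve approach under the assumption of piecewise linear change in EQ-5D-5L-index values over time", plans multiple imputation, and says that "the uncertainty of the ICER will be assessed by performing sensitivity analysis including application of bootstrapping techniques". Neither document attaches a baseline, stratum or cluster term to this analysis, or says what the bootstrap resamples.

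**Design and data.** To avoid contamination, the groups must be handled by different primary care staff, and "this can only be achieved by randomizing municipalities (or health care districts" (Protocol, Design). Randomisation was stratified by number of inhabitants, in five strata (Amendment B). Baseline utility is collected: "Patient reported outcomes (EORTC QLQ-C30 and EQ-5D-5L) will be assessed at baseline, by the end of RT" (Protocol, Outcomes and assessments).

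**EQ-5D-5L as an outcome.** The SAP (Primary analysis, Secondary analyses) gives it the primary-outcome mixed model, with baseline as a fixed effect and random effects for patients within cluster.

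**The concern.** The same questionnaire gets baseline and cluster terms when analysed as a score, and neither is stated once it becomes a QALY. Two separate consequences follow.

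1. **Baseline utility.** A QALY built as an area under the curve includes the baseline value and is correlated with it through every later visit. A plain difference in means therefore carries any chance imbalance in baseline utility into the denominator of the ICER. Randomisation keeps the expected imbalance at zero, so the cost is precision.
2. **Clustering.** If patients are resampled as though independent, within-municipality correlation in costs or QALYs is ignored. Some correlation in costs is plausible, because home care and nursing-home care are municipal services. Intervals and acceptability curves would then look too certain, and acceptability curves are a planned output.

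**Working it through.** The documents give no figure for the precision of the ICER, so there is nothing to reproduce. The checks below only gauge size.

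**A. Baseline utility**

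Inputs from the documents: visits at baseline, end of RT, then 4, 8, 16, 32 and 52 weeks later. Assumed: RT lasting 2 or 7 weeks; utility mean 0.7 and SD 0.20-0.25; equal correlation r between all visits. The value r = 0.5 is the SAP's figure for physical function, borrowed here.

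*No deaths, by hand.* With trapezoid weights w in weeks, the slope of the area on baseline is w0 + r(T - w0), and its variance in SD-squared units is rT² + (1 - r)Σw².

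- RT 2 weeks: w = 1, 3, 4, 6, 12, 18, 10; T = 54; Σw² = 630. Slope = 1 + 0.5 × 53 = 27.5 weeks = 0.53 QALY per unit. Variance = 1458 + 315 = 1773. R² = 27.5²/1773 = 0.43.
- RT 7 weeks: w = 3.5, 5.5, 4, 6, 12, 18, 10; T = 59; Σw² = 662.5. Slope = 3.5 + 0.5 × 55.5 = 31.25 weeks = 0.60. Variance = 1740.5 + 331.25 = 2071.75. R² = 0.47.

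Baseline's own weight is small (1 to 3.5 weeks); most of the carry-over comes through the correlation.

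*With deaths, by simulation.* Assumed: utility 0 after death (the documents do not say how deaths enter), one-year mortality 10-40%, and hazard ratio 1-2 per SD lower baseline utility. Mortality is unlikely to be negligible, since "Palliative RT represents about 60 % of the patients" at the main centre.

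- r = 0.5: R² 0.09-0.41, carry-over 0.41-0.95. Cut in the standard error = 1 - √(1 - R²) = 5-23%.
- r = 0.3: R² 0.04-0.28. r = 0.7: R² 0.16-0.58.

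*Typical imbalance.* The SD of the baseline difference is SD × √(2/93 × DE), with 93 enrolled per arm and DE as in B. This runs from 0.20 × √(2/93 × 1.07) = 0.030 to 0.25 × √(2/93 × 2.19) = 0.054. A 1-SD imbalance shifts incremental QALYs by 0.030 × 0.41 = 0.012 up to 0.054 × 0.95 = 0.051.

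**B. Clustering, only if patients are resampled**

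Inputs from the documents: ICC 5% (Protocol, Sample size) and 10% (SAP, Sample size), both for physical function; 138 evaluable patients, so 69 per arm; enrolment target 93 per arm; 32 clusters, one withdrawn and four more empty at the February 2020 count (Amendment B). Assumed: arm splits of 16/15, 14/13 or 16/11 clusters; cluster-size CV 0.5-0.9; ICC 1% as a low case.

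DE = average over arms of 1 + ((1 + CV²) × n/k - 1) × ICC. Coverage of a nominal 95% interval for a mean difference = 2Φ(1.96/√DE) - 1.

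- *Best case at ICC 5%* (69 per arm, CV 0.5, 16/15): DE = (1.2195 + 1.2375)/2 = 1.229; coverage 92.3%.
- *Worst case at ICC 10%* (69 per arm, CV 0.9, 16/11): DE = (1.681 + 2.035)/2 = 1.858; coverage 85.0%.

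| ICC | 69 per arm | 93 per arm |
|---|---|---|
| 1% | 94-94% | 94-94% |
| 5% | 90-92% | 88-91% |
| 10% | 85-90% | 81-87% |

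*Simulation cross-check* (69 per arm, 14 clusters per arm, sizes 1-11, normal outcome, 2000 trials):

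- ICC 5%: patient-bootstrap SE 0.0336 against a true 0.0385 (13% too small), coverage 89.4%.
- ICC 10%: 0.0334 against 0.0432 (23% too small), coverage 86.5%.
- A plain cluster percentile bootstrap covered 92.6% and 91.4%, so naming the cluster as the unit is not enough with this few clusters.

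**The case against.** **The wording is generic.** A ratio of mean differences is the textbook ICER, and regression-adjusted means would fit it. That stands: a reader might infer that the plan rejects adjustment, but the documents only leave it unstated. The promise of covariate adjustment in the protocol's Statistics section does not fill the gap, because it closes the mixed-model paragraph and the economic paragraph follows with its own definition. Nor does the SAP's trend model for continuous secondary outcomes, which is for repeated assessments; a QALY is one value per patient.

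**Under-coverage is doubly conditional.** It needs patient resampling, which is not stated, and a material ICC for costs or QALYs, which is not given. That also stands. A reader might infer that the planned intervals are invalid, but a cluster bootstrap is compatible with the text.

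**The low end stacks worst cases.** Coverage of 81-82% needs ICC 10%, CV 0.9, 93 analysed per arm and all five lost municipalities in one arm. The documents do not say which arms lost clusters, and four were empty only at that count. With 69 per arm the same cell gives 85%, although imputation could bring the analysed number nearer 93.

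**Stratification is left out.** In an illustration with 16 clusters and 84 patients per arm, and half the between-cluster variance lying between strata, patient-level coverage was 93% (ICC 5%) and 91% (ICC 10%), against 90% and 86% with none between strata. The true share is unknown.

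**It is a pilot.** The primary analysis already has baseline and cluster terms. But the ICER is a named secondary outcome, and the protocol says analyses will be pre-planned.

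**Conclusion.** The concern holds as a gap in the stated method, of modest weight. Incremental QALYs and costs are differences in arm means with no adjustment stated, and the bootstrap has no stated unit, in a stratified cluster-randomised trial that models EQ-5D-5L with both baseline and cluster.

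- **Baseline half:** avoidable noise. At r = 0.5 and 10-40% one-year mortality, about 9-41% of patient-level QALY variance could be removed; the range moves with both assumptions. A claim of bias is not supported.
- **Clustering half:** only if patients are resampled. Coverage is then roughly 85-92% on borrowed ICCs of 5-10% with 69 analysed per arm, somewhat lower with 93, nearer nominal if stratification absorbs between-cluster variance, and little affected near 1%.

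These coverage figures concern a mean difference, not the ratio. They are illustrative and do not validate the full model proposed below. Only absence from the protocol and SAP is claimed; the separate protocol paper that they cite was not available.

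**What to change.** In the SAP's Economic evaluation:

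1. Estimate incremental QALYs by regression on group, baseline EQ-5D-5L index and randomisation stratum, and incremental costs with stratum, both accounting for cluster. Form the ICER from the adjusted differences.
2. Name one cluster-respecting uncertainty method with a small-sample correction. The lightest is a mixed model for net benefit at each threshold, with a random cluster effect and small-sample degrees of freedom, since the SAP already uses that model family. The alternative is a corrected cluster bootstrap. Avoid an uncorrected cluster percentile bootstrap.
3. Keep each patient's cost and QALY paired, and say how the method combines with multiple imputation.
4. Note a limitation shared with the SAP's primary model. The intervention begins before RT (Protocol, The intervention), while baseline is taken at the start of RT (Design) and may be completed up to the third or sixth treatment day (amendment of 29-02-20). Baseline EQ-5D-5L may therefore be recorded after the intervention has begun.

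The cost is SAP wording and some programming, more if a bootstrap is nested with imputation. No new data are needed. Intervals may widen from clustering, while baseline adjustment narrows the QALY part.

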## User involvement

User involvement is essential for this project. At SI, a group of four user representatives is established, and have participated in the planning and conduct of the observational study. For the conduct of the present study, an additional representative from Board of senior citizens in Trondheim is contracted. These user representatives will participate in the design of the intervention and implementation procedures. They will further contribute during the study conduct, to the interpretation of results by evaluating the relevance for the users, and participate in the dissemination of results to the public, patients and relatives. Regular meetings are implemented and will continue during the overall study conduct.

## Ethics

The study was approved by The Regional Committee for Medical Research Ethics, Health Region South-East (2018/2515/REK sør-øst A) and the Data Protection Official for

Research, Innlandet Hospital Trust and Trondheim University Hospital. The pilot study will be performed according to the rules of the Helsinki-declaration. Participation will not inflict upon the patients' cancer treatment and not imply any health risks or deviation from good clinical practice. Patients in the control group will receive care according to routine. However, a more thorough assessment followed by advice according to findings may, however, contribute to improved care. Written informed consent will be provided.

## Protocol amendment – 29-02-20

### **Adjustment of inclusion criteria**

---

We have realized that some patients are referred for radiotherapy for a cancer disease that has not been confirmed histologically or cytologically. In these cases, the referring oncologist has affirmed the malignant diagnosis based on medical history, imaging and blood analyses.

As participating in the study does not have any impact on the patients' cancer treatment, and neither the intervention, its results, or the patients potential benefit of the intervention program are in any way dependent on how the cancer diagnosis has been confirmed, we have decided to make a minor change of the inclusion criteria.

Formerly stated criteria for eligibility (according to original protocol)

